### 2.1.2. Natural History and Stages of the T1D Disease Process

Much is known about the natural history of the T1D disease process. Individuals with T1D have genetic susceptibility for disease; indeed, relatives of individuals with T1D are at much greater risk of developing disease. In the general population, approximately 0.3% of individuals will develop T1D. In contrast, those with a relative with T1D have a 5% risk of disease – a 15-fold increase. Further risk stratification among family members depends upon genetic, immune, and metabolic data.

Beta cell destruction is initiated in genetically susceptible individuals years before clinical onset of disease. The autoimmune process that causes beta cell destruction is clinically silent and can only be identified by the detection of autoantibodies in the blood, such as islet cell antibodies (ICA), and autoantibodies to glutamic acid decarboxylase (GAD65Ab), islet antigen 2 (IA-2Ab/ICA512), insulin (mIAA), zinc transporter 8 (ZnT8Ab), and others. Continued immune-mediated beta cell destruction involving both B and T cells occurs until physiologic insulin demand cannot be met by the remaining beta cells. Impaired insulin secretion is accompanied by progression from normal to abnormal glucose tolerance (both of which are asymptomatic states), until more severe hyperglycemia occurs associated with classic symptoms of polyuria and polydipsia and thus clinically overt disease.

Data gathered from multiple studies during the past 35 years are remarkably concordant with regard to the progression from development of autoantibodies to clinically overt disease. These data, whether from studies of longitudinal cohorts followed from birth or cross-sectionally identified populations at risk, indicate that essentially all genetically susceptible individuals with multiple autoantibodies (whether or not a relative) will eventually progress to clinical disease. Thus, T1D is considered to have started with the presence of 2 or more autoantibodies. The presence of two or more autoantibodies with normal glucose tolerance is defined as Stage 1 T1D. Stage 2 T1D is the presence of two or more antibodies with abnormal glucose tolerance, and Stage 3 T1D is clinically overt disease.

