### **3.3.1. Inclusion Criteria**

Study participants must be or have:

1. A participant in TrialNet Pathway to Prevention Study (TN01).
2. Age  $\geq$  3 years at the time of randomization in this trial.
3. Willing to provide informed consent or, if the participant is <18 years of age, have a parent or legal guardian provide informed consent.
4. Normal glucose tolerance by OGTT within 7 weeks (no more than 52 days) prior to randomization. If previous abnormal glucose tolerance, has had two consecutive OGTTs with normal glucose tolerance:
  - a. Fasting plasma glucose < 110 mg/dL (6.1 mmol/L), and
  - b. 2-hour plasma glucose <140 mg/dL (7.8 mmol/L), and

- c. 30, 60, and 90 minute value on OGTT < 200 mg/dL (11.1 mmol/L).
5. Two or more diabetes-related autoantibodies present on two separate samples, one of which was drawn within the past six months (210 days). Confirmation does not have to involve the same 2 autoantibodies.
6. Weight  $\geq$  12 kg at the time of screening.
7. If a female participant with reproductive potential, willing to avoid pregnancy and undergo pregnancy testing prior to randomization and at each study visit.
8. Anticipated ability to swallow study medication.

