### **8.1. Primary Outcome**

The primary outcome is the elapsed time from random treatment assignment to the development of confirmed abnormal glucose tolerance or clinical diabetes among those enrolled in the primary analysis cohort consisting of participants with islet cell autoimmunity and absence of metabolic abnormalities (normal OGTT). The date of the confirmatory abnormal OGTT or diabetes will be considered as the date of reaching these study endpoints. It is expected that abnormal glucose tolerance will be detected prior to diabetes onset by OGTT; however, the presence of diabetes, without a previous abnormal

OGTT, is also considered an endpoint.

While the hydroxychloroquine prevention study is ongoing, any participant who has progressed to abnormal glucose tolerance will have met the primary endpoint criteria. These participants who have developed abnormal glucose tolerance but have not progressed to Stage 3 T1D will have the option to remain in this study without further therapy; they will receive close monitoring and safety assessments until the development of Stage 3 T1D (clinical diabetes) or until they enroll in another clinical trial, whichever comes first.

The study endpoint is realized with either confirmed OGTT criteria for abnormal glucose tolerance or diabetes or clinical criteria for diabetes.

OGTT criteria for abnormal glucose tolerance or diabetes:

The presence of an OGTT consistent with impaired glucose tolerance or diabetes on two sequential dates. A participant with abnormal glucose tolerance or diabetes on an OGTT should undergo a repeat OGTT as soon as possible, but no less than one day apart. Aim to repeat within one month.

The definition of abnormal glucose tolerance is:

- a. Fasting plasma glucose  $\geq 110$  mg/dL (6.1 mmol/L) and  $< 126$  mg/dL (7.0 mmol/L), or
- b. 2 hour plasma glucose  $\geq 140$  mg/dL (7.8 mmol/L) and  $< 200$  mg/dl (11.1 mmol/L), or
- c. 30, 60, 90 minute plasma glucose during OGTT  $\geq 200$  mg/dL (11.1 mmol/L).

Criteria for Diabetes Diagnosis:

- A. Diabetic Ketoacidosis (DKA) or unequivocally symptomatic\* AND at least one of the following:
- 1) Random glucose  $\geq 200$  mg/dl (11.1 mmol/L) OR
  - 2) Fasting Glucose  $\geq 126$  mg/dl (7.0 mmol/L) OR
  - 3) OGTT = diabetic\*\* OR
  - 4) HbA1C  $\geq 6.5\%$ .

\*Unequivocal symptoms: Severe/persistent polyuria, polydipsia and/or significant unexplained weight loss

\*\*A diabetic OGTT is defined as:

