## 8.2. Primary Analysis

The primary objective of the study is to assess the effect of hydroxychloroquine therapy versus placebo on the risk of progression to Stage 2 or 3 T1D, which is measured from an OGTT or clinically diagnosed with confirmation.

Time to progression to Stage 2 or 3 T1D will be calculated across participants within each treatment group. Time to T1D stage progression will be estimated based on Kaplan-Meier methodology, where participants who were "free of abnormal glucose tolerance and/or T1D" at their last follow-up will be censored at that time point.

This time-to-event outcome will be analyzed using a Cox proportional hazards regression model that stratifies by prior T1D prevention treatment (none vs. placebo vs. active therapy) and age at the time of randomization (<8 yr vs  $\geq$ 8 yr), where treatment effect in this model will be tested using the Wald statistic. Incorporating these as stratification factors in the Cox regression model will allow separate baseline hazard functions to be fitted for each stratum. We will further evaluate differences in event rates in those in the prior treatment stratification factor; specifically, we will assess if there are differential event rates in those enrolling after participation in another prevention trial and ensure that this is accommodated by corresponding stratification in the Cox regression model.

In addition to stratifying on these factors, we will also evaluate if they are effect modifiers on any differences observed in the time to T1D stage progression between these prior treatment groups; i.e., we will formally test for interactions of treatment effect with prior treatment for T1D prevention as well as age on time to T1D stage progression (i.e. progression from Stage 1 to Stages 2 or 3 T1D).

Proportional hazards can be tested to ensure that we can assume that these effects will be parallel. If the assumption of proportional hazard is not appropriate, the data will be examined to determine the cause of non-proportional hazard, such as the presence of a decaying, diverging, or crossing effect of hazard ratios over time. Based on the cause of the non-proportional hazard, post-hoc analyses such as frailty models, parametric models, or models with interactions and time-dependent covariates may be employed.

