Criteria for diabetes_onset (T1DM) are based on glucose testing, or the presence of unequivocal hyperglycemia with acute metabolic decompensation (diabetic ketoacidosis). One of the following criteria must be met on two occasions as soon as possible but no less than one day apart for diabetes to be defined: 1. Symptoms of diabetes plus casual plasma glucose concentration ≥ 200 mg/dL (11.1 mmol/L). Casual is defined as any time of day without regard to time since last meal. The classic symptoms of diabetes include polyuria, polydipsia, and unexplained weight loss. 2. Fasting plasma glucose ≥ 126 mg/dL (7 mmol/L). Fasting is defined as no caloric intake for at least 8 hours. 3. 2 hour plasma glucose ≥ 200 mg/dL (11.1 mmol/L). The test should be performed using a glucose load containing the equivalent of 1.75g/kg body weight to a maximum of 75g anhydrous glucose dissolved in water. It is preferred that at least one of the two testing occasions involve an OGTT. Cases identified will be confirmed as having diabetes if the glucose values to make these determinations were obtained in a TrialNet laboratory as part of an OGTT. Cases diagnosed with diabetes by symptoms and casual glucose ≥ 200 mg/dL or by other criteria than the above will be adjudicated by the TrialNet Endpoint Adjudication Committee.

The date of arriving at the study endpoint is the date of the second occasion that meets either of the above criteria or the date in which the participant presented in a state of DKA.

3. Primary Analysis

The study design is a randomized double-blind placebo-controlled trial. The primary objective of the study is to assess the effect of hydroxychloroquine versus placebo on the risk of developing abnormal glucose tolerance (AGT) as measured from an OGTT.

The cumulative incidence of AGT over time since randomization within each treatment group will be estimated from a Kaplan-Meier estimate of the "AGT-free" survival function. Time-to-AGT was discretized to 6-month times in keeping with the OGTT schedule. The difference between groups in the cumulative incidence functions, and the associated hazard functions, will be tested at the 0.05 level, two-sided, using the Cox regression including age as a covariate (1, 5). The critical value for the test statistic, and confidence intervals in this primary analysis will be determined by the group-sequential procedure.

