Data from the TrialNet Pathway to Prevention Study may be used to determine participant eligibility. Outcomes from other studies may be used in meta-analyses, but not in the evaluation of this study's efficacy.

4. Secondary Outcomes and Analyses

4.1 Subgroup analyses.

Subgroup analyses will be conducted comparing the effects of hydroxychloroquine versus placebo on the risk of AGT with a test of the group by subgroup factor interaction in a Cox proportional hazard (PH) Model. Subgroups of the population by age (classified appropriately), gender, race/ethnicity (white, nonwhite and Hispanic yes/no), and specific antibody status at baseline. Differences in the treatment effect between subgroups will be tested using Likelihood Ratio Test (LRT) in a Cox PH model (1).

4.2 Covariate analyses.

Similar analyses will be conducted using the values of quantitative baseline factors. They include age, weight, BMI, HbA1c, HLA (DR3/4 vs. others), autoantibody titers, basal C-peptide, stimulated C-peptide (peak and AUC), glucose (fasting, 2-hour, AUC and measures of insulin secretory rate (0-30 min) and sensitivity (ISI) (6,7) modeled from the OGTT) at study entry. The dependence of the treatment effect on the quantitative levels of a covariate will also be assessed by a covariate by treatment group interaction in a PH model. The ISI can also inform on the treatment effect independent of C-peptide.

The association of demographic, genetic, immunologic, metabolic, and lifestyle factors, the presence of illness and concomitant meds, both at baseline and over time, with the risk of AGT onset will be assessed in Cox PH Models over time. The effects of changes in longitudinal factors on AGT risk will be assessed using time-dependent covariates for these factors.

Using a step-up procedure additional covariates will be tested and included in the model only if they improve the log-likelihood at 0.10 level (2-sided). This will be accomplished with the treatment assignment variable included but the inclusion/exclusion of the candidate covariates will be completely independent of the treatment variable's impact on the model. The LRT associated with treatment variable in the full, adjusted model will be used for the test of treatment effect described in the previous paragraph. Thus, the adjustment of the significance level, as with multiple testing, is unnecessary.

4.3 Longitudinal analyses.

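### Optional gain: neither primary Cox model uses the baseline OGTT glucose every participant has, although the endpoint is mainly a glucose threshold on the same test

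*Protocol*

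**What the plan says.** **Primary model.** Protocol 8.2: "This time-to-event outcome will be analyzed using a Cox proportional hazards regression model that stratifies by prior T1D prevention treatment" and by age at randomization (under 8 versus 8 or older), with a Wald test of treatment. SAP section 3 tests the groups "using the Cox regression including age as a covariate" and mentions no stratification. The two models differ, and neither has a glucose term.

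**Baseline data.** Protocol 3.3.1 requires of every participant: "Normal glucose tolerance by OGTT within 7 weeks (no more than 52 days) prior to randomization". Normal means fasting glucose below 110, 2-hour below 140, and 30-, 60- and 90-minute values below 200 mg/dL.

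**Endpoint.** Protocol 8.1 uses the same lines on the same test, with confirmation: "The presence of an OGTT consistent with impaired glucose tolerance or diabetes on two sequential dates". Clinical diabetes without an earlier abnormal OGTT also counts.

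**Where baseline glucose does appear.** SAP 4.2 lists its candidates this way: "They include age, weight, BMI, HbA1c, HLA (DR3/4 vs. others), autoantibody titers, basal C-peptide, stimulated C-peptide (peak and AUC), glucose (fasting, 2-hour, AUC", plus other OGTT measures. They enter covariate-by-treatment interaction analyses and a step-up in which "additional covariates will be tested and included in the model only if they improve the log-likelihood at 0.10 level (2-sided"). The end of Protocol 8.2 allows further factors to be defined before unmasking but names none.

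**Prognostic value.** Protocol 2.1.2 is qualitative: "Further risk stratification among family members depends upon genetic, immune, and metabolic data". No hazard ratio for baseline glucose is given anywhere.

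**The concern.** Everyone starts below the endpoint lines, but not equally far below. A participant with a 2-hour value of 135 mg/dL has 5 mg/dL to go before meeting that criterion; one at 90 has 50. If that distance predicts time to progression, leaving it out of a Cox model pulls the estimated treatment hazard ratio toward 1 and gives up some power. It also leaves the primary comparison open to chance imbalance in starting glucose, with only 66 participants on placebo.

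The plan already accepts this reasoning for age, which it treats as prognostic and builds into the randomization and the primary model. It cites metabolic data as relevant to risk but brings no metabolic variable into the primary model. What is at stake is efficiency; the validity of the planned test is not in question.

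**Working it through.** **1. Reproduce the plan's power.** Inputs from Protocol 8.4 and 8.5, repeated in SAP sections 5 and 6: hazard ratio 0.50, 80 events in total, 2:1 allocation, two-sided 0.05, final critical value 1.969.

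Schoenfeld: power = Φ(√(D·p·(1−p))·|ln HR| − z), with D = 80 and p(1−p) = 1/3 × 2/3 = 2/9.

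- √(80 × 2/9) × ln 2 = 4.216 × 0.693 = 2.923
- with z = 1.960: Φ(0.963) = 83.2%
- with z = 1.969: Φ(0.954) = 83.0%

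The stated 83% is right, and the formula has no covariate term. (The timing paragraph of SAP section 7 gives a different event trigger. That is a separate conflict; 80 total events is used here.)

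**2. Check that the events are reachable.** Placebo hazard = −ln(0.60)/2 = 0.2554 per year. The two-year risk on active treatment at HR 0.50 is 1 − 0.60^0.5 = 22.5%, as stated. With four years of uniform accrual and two more of follow-up, expected events at six years are 85.8 with 10% two-year dropout and 94.3 with none. Both exceed 80.

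**3. Simulate with and without the covariate.** Assumption, not in the documents: the hazard ratio per standard deviation (SD) of baseline glucose among enrolled participants. Marginal two-year risks are held at the plan's 40% and 22.5%, with analysis at the 80th event and critical value 1.969.

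| Assumed HR per SD | Power without | Power with | Gain (points) | Gain across repeat simulations |
|---|---|---|---|---|
| 1.0 (not prognostic) | 86.1% | 86.0% | −0.1 | −0.6 to −0.1 |
| 1.3 | 85.6% | 86.8% | 1.2 | 0.7 to 1.4 |
| 1.5 | 85.3% | 88.7% | 3.4 | 2.8 to 3.4 |
| 2.0 | 83.9% | 91.1% | 7.2 | 6.9 to 7.6 |

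With 2,500 trials per row, as in the repeats, the Monte Carlo standard error of one power figure is √(0.86 × 0.14/2500) ≈ 0.7 points. Rejection under the null with adjustment was 4.8–5.2%, and 4.2–5.4% in a repeat with 1,500 trials per row (standard error about 0.6 points). Both are consistent with 5%.

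The simulated power without the covariate sits about 3 points above Schoenfeld because, at HR 0.50, events split more evenly between arms than 2:1. The rows should therefore be read as differences.

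**4. Sensitivity to calibration (4,000 trials per row).**

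- Unadjusted HR held near 0.50: 85.8% to 87.1% at HR per SD 1.35, 86.1% to 90.3% at 1.65, and 88.0% to 94.2% at 2.0.
- 0.50 taken as the glucose-conditional HR: 83.6% to 85.2%, 80.6% to 85.1%, and 74.2% to 85.4% at the same values. The average unadjusted HR drifts to 0.51, 0.53 and 0.55.
- Event times moved to 6-month visits, in line with SAP section 3, at HR per SD 1.65 and conditional HR 0.50: 77.3% to 82.0%. Both powers fall and the gain stays near 5 points.

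Interim stopping was not simulated in step 4.

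**The case against.** The strongest reply is that nothing is wrong. The design power reproduces, the primary model in the Protocol respects the randomization strata, and stopping there is a normal choice. At the plan's own event rates, unadjusted power in the step 3 table stays at or above 83.9%. That stands, and it is why this point is optional.

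Three stronger readings are tempting, and the documents do not support them.

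- *The trial is underpowered.* A reader might infer this from the 74.2% row in step 4. That row takes 0.50 as a glucose-conditional effect; the plan states its effect through unconditional two-year rates of 40% and 22.5%.
- *The SAP ignores baseline glucose or uses it post hoc.* SAP 4.2 prespecifies the candidates, the 0.10 entry rule and a treatment test in the resulting model. The selection is data-driven but planned. It does not, however, put glucose into the primary test.
- *Power cannot be obtained in any other way.* The final analysis is event-driven, and both documents allow follow-up to be lengthened to reach the required events.

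Two further objections limit the size of the claim. Eligibility cuts off baseline glucose at the endpoint lines, which narrows its spread and makes the larger hazard ratios per SD less safe to assume. And nothing in the documents favours 2-hour glucose over fasting or AUC glucose. Both stand. The first is a reason to give weight to the 1.3 row; the second means the choice must be made and fixed in advance.

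**Conclusion.** The point holds as a low-cost improvement. Neither primary model includes a baseline measure that every participant has and that lies on the same scale as the main endpoint criteria. The direction of the benefit is consistent across calibrations: about 1 point of power at HR per SD 1.3, about 3 at 1.5 and about 7 at 2.0, with a loss under 1 point if glucose carries no information and type I error near 5%.

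The size rests wholly on an assumed prognostic strength, for a covariate modelled as normal with a constant log-linear effect. It also assumes 80 total events and the plan's 40% and 22.5% rates. No figure in the power section needs correcting on this account.

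**What to change.** Protocol 8.2 and SAP section 3 have to be reconciled in any case. When they are brought to the stratified Cox model of Protocol 8.2, and before unmasking:

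- Add one named continuous covariate to the primary model in both documents, for example 2-hour glucose from the qualifying OGTT.
- State that the primary hazard ratio is conditional on that covariate as well as the strata.
- Report the stratified model without it as a sensitivity analysis.
- Leave the SAP 4.2 step-up as secondary.

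No new data, visits or participants are needed. The covariate itself takes about a sentence in each document; reconciling the two models is a separate and larger edit. The statistical price is under 1 point of power if glucose proves uninformative, and a hazard ratio that must be read as conditional on baseline glucose.

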### 8.3. Secondary Outcomes and Analyses

A variety of secondary analyses are planned, including the following:

Time to progression to Stage 3 T1D (clinical diabetes) will also be evaluated. Those participants who progress to Stage 2 T1D (abnormal glucose tolerance) prior to developing clinical diabetes will also be included in the time to (Stage 3) T1D analyses. Any participants who develop abnormal glucose tolerance and enroll in another treatment trial or receive other prevention therapy prior to development of Stage 3 T1D will be censored at that time. The treatment arms will be compared in terms of the corresponding distributions of time to progression to Stage 3 T1D (clinical diabetes) using the same methods described for the primary endpoint. Subgroup analyses analogous to those described for time to the composite event definition of progression to Stage 2 **or** 3 T1D will be conducted on the endpoint of time to progression to Stage 3 T1D.

Longitudinal analyses will assess the effects of hydroxychloroquine versus placebo treatment on immunologic and metabolic markers over time up to the onset of progression to Stage 2 or 3 T1D. Differences between groups in the mean levels of quantitative factors over time will be assessed using a normal errors linear model for repeated measures. Differences between groups in the prevalence of qualitative factors over time will be assessed using generalized estimating equations for categorical measures. Generalized estimating equations may also be employed for the analysis of quantitative factors if the assumption of multivariate normal random errors is violated.

Immunologic and metabolic markers will be modeled to determine the effects of hydroxychloroquine versus placebo treatment while adjusting for participant characteristics for each follow-up time point of interest. For continuous endpoints that lend themselves to normal error linear models, ANOVA and ANCOVA models will be employed. Generalized linear modeling will be employed for dichotomous and categorical endpoints by using the most appropriate link functions. Longitudinal analyses may be employed in order to characterize the relationship among the repeated measures during the treatment period and possibly beyond. Due to the exploratory nature of the longitudinal modeling, treatment effect hypothesis testing will not be conducted.

The association of demographic, genetic, immunologic, metabolic, lifestyle factors, the presence of illness and concomitant medications, among others, both at baseline and over time, with the risk of T1D stage progression will be assessed in Cox regression models over time. The effects of changes in longitudinal factors on risk of progression will be assessed using time-dependent covariates for these factors. Analyses will be conducted separately within the hydroxychloroquine and placebo groups, and differences between groups in covariate effects (group by covariate interactions) will be assessed. Models will then be assessed within the two groups combined, taking account of any group by covariate interactions. Subgroup analyses will be conducted comparing the effects of hydroxychloroquine versus placebo on the risk of progression to Stage 2 or 3 T1D with a test of the group by subgroup factor interaction in a Cox proportional hazard (PH) Model. Specifically, we will evaluate potential differential effects of treatment in relation to other factors at baseline, including: age (both continuous as well as

categorical: children < 8 years of age vs.  $\geq$  8 years, as well as < 8 years vs. 8 to 12 years vs. adolescents [13-17 years] vs. adults [ $\geq$  18 years]), gender, race/ethnicity, whether or not they have a first degree relative (FDR) with T1D, and specific autoantibody status. Similar analyses will be conducted using the values of quantitative baseline metabolic and anthropometric factors such as weight, BMI, and the immunologic and metabolic factors described in Section 6 that include the autoantibody titers, basal C-peptide, stimulated C-peptide (peak and AUC mean), and measures of insulin resistance modeled from the OGTT. These potential effect modifiers, or interaction effects, will be evaluated both using tests of interaction in the Cox regression model as well as stratified analyses. In addition, we will evaluate differences in time to T1D stage progression across all randomized participants using multivariable Cox regression models with tests of interaction and stratified analyses to assess potential differential effects, based on whether or not participants were previously treated for T1D prevention.

Toxicity is defined as adverse events that are classified as either possibly, probably, or definitely related to study treatment. The maximum grade for each type of toxicity will be recorded for each participant, and frequency tables will be reviewed to determine toxicity patterns. In addition, we will review all adverse event data that is graded as 3, 4, or 5 and classified as either “unrelated” or “unlikely to be related” to study treatment in the event of an actual relationship developing. The incidence of severe (grade 3+) adverse events or toxicities will be described for each treatment arm, but will also be compared between the arms. Fisher’s exact tests will be used to quantitatively compare the incidence of severe as well as specific toxicities of interest between the treatment arms, and we will graphically assess differences in maximum grades observed for toxicities between the arms. These analyses will be useful in identifying potential toxicity patterns of interest and in planning future trials. We will also assess tolerability of hydroxychloroquine through assessing the proportion of patients who discontinue treatment due to adverse reactions or even those who refuse further treatment for lesser toxicities that inhibit their willingness to continue participation on the trial. These tolerability measures will be assessed within each of the treatment arms and we will explore differences in these measures between the arms. All participants who have received at least one dose of any of the therapeutic agents in a treatment arm will be evaluable for toxicity and tolerability.

